6.1. Treatments Administration	
6.2. Concomitant Therapy	
7. Efficacy Assessments	
8. Safety Assessments	
9. Adverse Event reporting	
9.1. Definition and reports of Adverse Events.....	
9.2. Adverse event follow-up.....	
10. Criteria for the termination of the trials	
11. Statistical Considerations	

11.1.	Sample Size Determination
11.2.	Planned Statistical methods of analysis.....
11.2.1.	Efficacy analyses.....
11.2.2.	Safety analyses.....
11.2.3.	Additional analyses
11.2.4.	The level of significance
11.2.5.	Analysis Population
12.	Direct access to source data/documents
13.	Ethical considerations
14.	Data handling and keeping
15.	Financing and Insurance
16.	References.....

1. Synopsis

Protocol Title : The effects of high protein supplementation, core muscle rehabilitation and neuromuscular electrostimulation (NMES) on clinical outcomes in patients with prolonged mechanical ventilation (PMV)

Study Objectives :

To evaluate the benefit of high protein supplementation and core muscle rehabilitation and trunk NMES intervention for weaning in PMV patients.

Investigational product(s) :

high protein supplementation (1.5 g/kg/day protein)

core muscle rehabilitation (sitting for 30 minutes, twice per day, 5 days per week)

trunk NMES intervention (Electrodes were placed on back designed to activate latissimus dorsi and abdominal wall designed to activate the transversus abdominis and internal and external oblique muscles.

Electrical muscle stimulation was performed by using a using a commercial stimulator (GEMORE, GM300E, Taipei, Taiwan)

with biphasic waves at a simulation frequency of 30 Hz and pulse width of 400s, cycling 2s on and 4s off. Electrical muscle stimulation intensity was gradually increased until a visible muscle contraction was observed (median 60 mA [range 50–65 mA].)

Development Phase : I II III IV 其它 _____ 不適用

Study Design :

1. Experimental Group :

1. High protein supplementation
2. High protein supplementation + Core muscle rehabilitation
3. High protein supplementation + Core muscle rehabilitation + trunk NMES intervention

Control Group :

Usual care in Respiratory Care Center

2. Blinding : Open Evaluator-blind Single-blind(patient) Double-blind(patient+PI)
 Double Dummy Other _____

3. Randomization: Yes No

4. Parallel design Crossover design Other _____ Not applicable

5. Treatment Period : 3 weeks Not applicable

6. Study Period: 2 years

6. Dose adjustment : Mandatory Selectively No Not applicable

7. Study location : Single Multi-center Global

Endpoints (Outcome measure) :

1. Primary endpoint:

Weaning rate (weaning success defined as weaning from ventilator for 5 consecutive days)

2. Secondary endpoints:

In hospital mortality, Length of mechanical ventilator usage,

Length of ICU stay and total length of hospitalization,

Serum albumin level improvement, Creatinine clearance rate

Inclusion/Exclusion Criteria :

Patients

Patients (age \geq 20 years old) on mechanical ventilator for more than 21 days were recruited from the respiratory care center (RCC). of Chang Gung Memorial Hospital in Taiwan.

The **inclusion criteria** were as follows:

1. age \geq 20 years old
2. using mechanical ventilator for more than 21 days (including patients under tracheostomy or endotracheal tube)
3. stable clinical condition, without using inotropic agent
(arterial blood gas pH 7.35–7.45, $\text{PaO}_2 \geq 60$ mm Hg at FiO_2 40%, absence of signs and symptoms of uncontrolled infection, and hemodynamic stability)
4. maximal inspiratory pressure (MIP) < 30 mmHg
5. under enteral nutrition (EN) via NG tube.

The **exclusion criteria** were as follows:

1. Acute infection and sepsis (fever up to 38.5 degree)
2. Severe neuromuscular disease, or uncontrolled epilepsy
3. Bony fracture or DVT history
4. Wound over the abdomen
5. Congestive heart failure with EF < 40% or using pacemaker
6. BMI > 35 kg/M², or severe edema
7. Patients with hepatic failure, rapid progressed malignancy, or pregnancy were also excluded.
8. Under parenteral nutrition (PN)
9. Use pacemaker

[figure not shown]
Patient's identification will be recorded as a study code, which will not be mentioned in the publication.

Study Procedures :

Eligible patients with informed consents will randomly stratify into four groups: (1) Usual care (UC), (2) UC + high protein diet (HP), (3) UC + HP + core muscle rehabilitation, (4) UC + HP + core muscle rehabilitation + neuromuscular electric stimulation (NMES). Ten patients will be assigned to UC group. Thirty patients will be included in another 3 group. An independent researcher from Chang Gung Medical Foundation Clinical Trial Center makes random allocation cards using computer-generated random numbers. We used sequential sealed envelopes were prepared by an independent investigator ([name]), with one chosen randomly by study nurse for each subject. The subjects were then assigned to each group according to the label in the envelope. The total daily caloric intake is based on the suggestion of nutritionist. The HP groups will maintain unchanged total daily caloric intake and increasing protein content to 1.5g/kg/day. The specific formulas were chosen for their different energy and protein requirement (mainly Nutri-Aid, or NU-PEP HN, according to patients' digestion, and may add Whey-Aid if necessary (above formula are available in CGMH currently)). We will maintain the nutrition strategies for 21 days according to patients' weaning condition. Protein provision was not reduced in case of renal failure. Core muscle rehabilitation is sitting on bedside with or without aids, for 30 minutes, twice per day, 5 days per week, for 3 weeks. NMES was applied for 30 min, twice per day, 5 days per week, for 3 weeks via surface rectangular electrodes. Electrodes were placed on back designed to activate latissimus dorsi and abdominal wall designed to activate the transversus abdominis and internal and

external oblique muscles as previously McCaughey et al described³⁷. Electrical muscle stimulation was performed by using a commercial stimulator (GEMORE, GM300E, Taipei, Taiwan) with biphasic waves at a simulation frequency of 30 Hz and pulse width of 400s, cycling 2s on and 4s off. Electrical muscle stimulation intensity was gradually increased until a visible muscle contraction was observed (median 60 mA [range 50–65 mA]).

The age, gender, smoking history, diagnosis, length of mechanical ventilator use, APACHE II will be recorded. The pulmonary performance, including tidal volume, maximal inspiratory pressure (MIP), cough function, peak inspiratory pressure (PIP), positive end-expiratory pressure (PEEP), lung compliance, airway resistance, blood gas analysis, Barthel index, serum albumin, creatinine, electrolytes will record before, during (twice per week) and after intervention. We also follow the outcome of hospitalization, including the weaning rate, mortality, length of mechanical ventilator use, length of ICU stay and total length of hospitalization. We will further evaluate the diaphragm movement. Ultrasound was performed at the end of exhalation (without stimulation) to measure the thickness of the diaphragm, twice per week of participation, and then weekly until RCC discharge. All measurements were taken from muscles on the right-hand side of the participant by the same assessor at all assessment sessions. For the diaphragm, the probe was placed parallel to the anterior axillary line in the intercostal space between the 9th and 10th rib and moved in the cranial and caudal directions until the pleural line was identified. From this point, the probe was moved approximately 1 or 2 intercostal spaces lower to identify the costal diaphragm in the zone of apposition. In all measurements, the probe was placed perpendicular to the skin. We will analyze the diaphragm movement, thickness and the correlation with successful weaning rate.

Concomitant Treatments : 不適用

1. Concomitant Therapy :

2. Prohibited Therapy :

Statistical Methods :

1. Main study Hypothesis : Equality Superiority Non-inferiority
 Equivalence Other _____

2. Estimated Sample Size : 100_

3. Efficacy assessment group : Intent-to-treat (ITT) Per-Protocol (PP)
 Other _____

ITT: We include all eligible patients who meet the criteria had signed informed consents to participate this study.

4. Interim analysis : Yes No

Statistical methods : Categorical variables were described using counts (percentages).
 Parametric data were expressed as means \pm standard deviation (SD). Among the group

comparisons, one-way analysis of variance (ANOVA) followed by Dunnett's test, where appropriate, was used to determine the statistical significance of the difference between means. The follow-up parametric data were compared using the paired student's t-test. Non-parametric data were determined by chi-squared tests. Analyses of primary and secondary outcomes are performed with the use of time-to-event methods according to the intention-to-treat principle. All analyses were two-sided, and $p<0.05$ was considered statistically significant. Statistical analyses were performed using Prism version 5 (GraphPad Software Inc., La Jolla, CA, USA).

5. Handling of Missing Data :

Omit the cases with missing data and analyze the remaining data.

2. Introduction and Rationale

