2.5 Regulatory

This study will be conducted in compliance with the protocol approved by the Institutional Review Board, and according to Good Clinical Practice standards. No deviation from the protocol will be implemented without the prior review and approval of the IRB except where

it may be necessary to eliminate an immediate hazard to a research subject. In such case, the deviation will be reported to the IRB as soon as possible.

3. Objectives and Endpoints

3.1 Study Objectives:

3.1.1 Primary objective:

To evaluate the benefit of high protein supplementation and core muscle rehabilitation and trunk NMES intervention in weaning from ventilator

3.1.2 Secondary objectives:

The impact of renal function and digestion status after high protein intake
The benefit in nutrition status and diaphragm weakness and the correlation to weaning status

3.1.3 Other exploratory objectives (if any):

1.2 Study endpoints:

3.2.1 Primary endpoint:

Weaning rate

(weaning success defined as weaning from ventilator for 5 consecutive days)

3.2.2 Secondary endpoints:

In hospital mortality, Length of mechanical ventilator usage,
Length of ICU stay and total length of hospitalization,
Serum albumin level improvement, Creatinine clearance rate

3.2.3 Other exploratory endpoints (if any):

4. Study Design

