4.3 Schedule of Activities

Time-Event scheme :

Phase	Screening	Treatment	4±1	6~7	Treatment	8~10	11±1	Treatment	13~14	Treatment	15~17	18±1	Treatment	20~21	Follow-up	22~27	28±1	
Day	0-1	1~3	4±1	6~7	8~10	11±1	13~14	15~17	18±1	20~21	22~27	28±1						
In-hospital visit	X	X	X		X	X		X	X	X	X	X	X	X	X	X	X	
Screening/Administrative/Safety																		
ICF/assent form	X																	
Inclusion/Exclusion criteria	X																	
Medical and surgical history, demographics	X																	
Physical exam	X		X				X				X				X			
Vital signs	X	X	X				X				X			X		X		
Height and body weight	X		X				X				X			X		X		
Pulmonary performance (ventilator)	X		X				X				X			X		X		
Laboratory study	X		X				X				X			X		X		
Barthel index	X																	
Echo for diaphragm evaluation	X		X				X				X			X		X		
Randomization/Administration																		
Randomization	X																	
Administration of high protein diet	X	X	X	X	X	X	X	X	X	X	X	X	X	X				
Administration of core muscle rehabilitation	X	X		X	X		X		X		X		X					
Administration of NMES	X	X		X	X		X		X		X		X					
Efficacy/Safety																		
Weaning profile	X		X				X				X	X	X	X		X		
Creatinine clearance rate	X		X				X				X	X	X	X		X		
Weaning rate													X	X				
Length of mechanical ventilator use													X	X		X		
Length of ICU stay													X	X		X		
Length of hospitalization													X	X		X		
In hospital Mortality													X	X				

5. Study Population

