6.2. Concomitant Therapy

Not Applicable

7. Efficacy Assessments

The age, gender, smoking history, diagnosis, length of mechanical ventilator use, APACHE II will be recorded initially.

The pulmonary performance, including tidal volume, maximal inspiratory pressure (MIP), cough function, peak inspiratory pressure (PIP), positive end-expiratory pressure (PEEP), lung compliance, airway resistance, blood gas analysis, Barthel index, serum albumin, creatinine, electrolytes will record before, during (twice per week) and after intervention.

We also follow the outcome of hospitalization, including the weaning rate, mortality, length of mechanical ventilator use, length of ICU stay and total length of hospitalization.

8. Safety Assessments

We will follow serum creatinine level and creatinine clearance rate weekly.

During core muscle rehabilitation and NMES, vital signs (heart rate, blood pressure, respiratory rate) and parameters in ventilator (tidal volume, FiO₂, peak airway pressure) will be monitored.

9. Adverse event reporting

We will report SAEs to the IRB of Chang Gung Medical Foundation according to the Serious Adverse Event Reporting Procedures and Guidelines as posted in the Clinical Trials Resource on the website of Chang Gung Medical Foundation IRB. SAE reports to the IRB should include the following information when calling the Medical Monitor:

- *Date and time of the SAE*
- *Date and time of the SAE report*
- *Name of reporter*
- *Call back phone number*
- *Affiliation/Institution conducting the study*
- *Protocol number*
- *Title of protocol*
- *Description of the SAE, including attribution to drug and expectedness*

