11.2.4 The level of significance

A p-value less than 0.05 was considered significant and was denoted by * and p-value less than 0.01 was denoted by **.

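### Serum albumin improvement is a secondary endpoint measured at several follow-ups, but no deciding visit is named and a paired t-test cannot show a difference between arms

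*Combined protocol and SAP*

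**What the plan says.** **Endpoint.** Section 3.2.2 and the synopsis include "Serum albumin level improvement, Creatinine clearance rate" in the secondary endpoints. Neither says what counts as improvement or when it is judged.

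**Timing.** Section 7, section 4.1 and the synopsis say "Barthel index, serum albumin, creatinine, electrolytes will record before, during (twice per week) and after intervention". The same sentence covers MIP, tidal volume, PIP, compliance and resistance. The synopsis gives "Treatment Period : 3 weeks". In the schedule (section 4.3), the laboratory row and the ventilator-performance row each carry one screening mark and about five later marks. Column alignment is uncertain in the text available.

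**Test and threshold.** The synopsis (Statistical methods) says "The follow-up parametric data were compared using the paired student's t-test" and "All analyses were two-sided, and $p<0.05$ was considered statistically significant". Section 11.2.4 adds "A p-value less than 0.05 was considered significant and was denoted by" an asterisk.

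**Other methods that could apply to albumin.**
- The same synopsis paragraph gives one-way ANOVA followed by Dunnett's test for group means.
- It also says "Analyses of primary and secondary outcomes are performed with the use of time-to-event methods according to the intention-to-treat principle", and albumin is a secondary outcome.
- Section 11.2 gives Student's t-test for parametric data and does not repeat the paired test.
- Section 11.2.1 assigns methods to weaning, survival and the duration outcomes, and does not mention albumin.

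**Missing data.** The synopsis drops cases with missing values, and section 11.4 excludes incomplete clinical data.

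**The concern.** A paired t-test uses two time points. With five to seven follow-ups, someone must decide which one is set against baseline, and the plan leaves that open until the data are in hand. The same albumin series could then be reported as improved or not improved depending on the visit picked, with an asterisk that suggests a 5% error rate.

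The second problem would remain even if a visit were named. A paired test asks whether albumin changed in the patients tested. The trial asks whether the assigned arm changed it. Albumin may rise or fall over three weeks in every arm, usual care included, so a significant change in one arm is not evidence for that arm's intervention.

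The alternative methods do not settle the matter. Dunnett's test compares arms but needs a visit. Time-to-event methods need an albumin event, and none is defined. Student's t-test in section 11.2 names neither a visit nor the pair of arms.

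**Working it through.** **1. Number of follow-ups.** By the text, 3 weeks x 2 per week = 6, or 7 if the record after intervention is a separate visit. By the schedule, 6 marks - 1 at screening = 5, taking albumin to belong to the laboratory row.

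**2. Arm sizes (section 11.1).** 10 in usual care and 30 in each of three other arms: 10 + 3 x 30 = 100, which reproduces the stated total. The only error figure in the plan is 0.05 per test.

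**3. Upper bound.** If the k tests were independent, the chance of at least one false positive would be 1 - 0.95^k: 22.6% for k = 5, 26.5% for k = 6 and 30.2% for k = 7. The real tests share a baseline and the same patients, so the rate is lower.

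**4. Simulation with no true change.** For each patient, draw a normal series with correlation rho^(days apart / 3.5). For follow-up j, let D_j be the change from baseline and t_j = mean(D_j) / (SD(D_j)/√n). Count a false positive if any |t_j| exceeds the two-sided 5% point of t on n - 1 degrees of freedom. There were 40,000 runs per case. Assumed days are 4, 11, 18, 21 and 28 for five visits; 4, 7, 11, 14, 18 and 21 for six; and these six plus 28 for seven.

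| Follow-ups tested | n | rho 0.5 | rho 0.7 | rho 0.9 |
|---|---|---|---|---|
| 1 (day 21) | 30 | 5.0% | 5.0% | 4.9% |
| 1 (day 21) | 10 | 5.1% | 4.8% | 5.0% |
| 5 | 30 | 17.7% | 16.9% | 15.5% |
| 5 | 10 | 18.6% | 17.8% | 16.1% |
| 6 | 30 | 18.9% | 17.9% | 16.4% |
| 6 | 10 | 19.8% | 18.8% | 17.1% |
| 7 | 30 | 21.2% | 19.8% | 18.2% |
| 7 | 10 | 22.3% | 20.7% | 19.2% |

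The one-visit rows return the plan's 5%. For five to seven visits the range is 15.5% to 22.3%, or about 15 to 22%. An equal correlation of 0.5 at all visits gives 18.2% to 24.4% for the same arm sizes.

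**5. Why a within-arm result does not stand for an arm effect.** A paired test is significant when the mean change, in SDs of change, exceeds t/√n. For n = 30 this is 2.045/√30 = 0.37; for n = 10 it is 2.262/√10 = 0.72. If the paired test is run within arms, an identical change of between 0.37 and 0.72 SD in every arm earns an asterisk in the 30-patient arms and none in usual care, with no difference between arms.

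**The case against.** The strongest reply is that the plan never describes visit-by-visit testing. The paired-test sentence does not say that all follow-ups are tested, or that the test is run within each arm. One before/after comparison fits it equally well, and section 11.2.2 describes the creatinine safety test in that form. On that reading the error rate is 5%. This stands. A reader might infer from the repeated measurements that the plan carries a built-in error rate of 15 to 22%; the documents do not support that. The figure is the risk left open by the missing rule, and it depends on assumed correlations.

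A reader might also carry the rate across arms. At six visits, 1 - (1 - 0.164)^4 = 51% to 1 - (1 - 0.189)^4 = 57%, using the 30-patient rates for all four arms. That needs every visit tested in every arm, which is nowhere written. Nor does the plan state a between-arm test at each visit, so no error rate for such a test can be charged to it.

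Third, section 11.1 calls the trial exploratory, albumin is not primary, and the ventilator measures appear in no endpoint list. This limits the weight of the point and confines it to albumin. It does not excuse a named endpoint with no visit and several candidate methods.

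Finally, a day 20-21 analysis of ventilator measures could be misleading, because they may not exist for patients already weaned or dead. That is correct, and it is why the same remedy should not be extended to them.

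**Conclusion.** The point holds for serum albumin. It is a named secondary endpoint with about five to seven follow-up values, no deciding visit, no settled method, and a paired test that cannot answer the question about arms. These facts come from the documents and need no assumption.

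The size is conditional: about 15 to 22% per measure per arm if each follow-up is tested against baseline, under AR(1) correlations of 0.5 to 0.9 per half-week and the planned arm sizes, against 5% for one named visit. The upper end belongs to the seven-visit reading of the text, and the five visits in the schedule give about 15 to 19%.

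In an exploratory trial this is a moderate matter. It does not touch the primary endpoint, but it should be settled before the data are examined.

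**What to change.** In the synopsis and section 11.2:

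- Make the deciding albumin analysis one mixed model for repeated measures with arm, visit, arm-by-visit and baseline albumin, using all recorded visits.
- Name the arm difference from usual care at the end of treatment (the day 20-21 column) as the only estimate that decides serum albumin improvement. There are three such contrasts, so state whether they are adjusted; the synopsis already names Dunnett's test for group comparisons.
- State that this replaces the rules in the synopsis and section 11.4 on dropping incomplete cases for this analysis, and that the time-to-event, paired and Student's t-test sentences do not apply to albumin. State the missing-at-random assumption and report the number of patients with a value at each visit, by arm.
- Show the other visits with confidence intervals and no asterisks.
- Report MIP, tidal volume, PIP, compliance and resistance descriptively, without asterisks.
- Reconcile the visit counts in the text and the schedule, and confirm that albumin is drawn in the day 20-21 column.

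The cost is plan wording and slightly more analysis work. SPSS, already named in section 11.2, fits the model. No extra patients are needed, and no new measurements if the day 20-21 sample is confirmed. Isolated changes at earlier visits become descriptive. The fix does not cure the small usual-care arm: with 10 against 30 patients, the standard error of a difference is √(1/10 + 1/30) = 0.37 SD before baseline adjustment, so intervals will be wide.

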4.2 Number of Patients

Evaluatable Number: 100

Enrolled Number: 80 (20% dropped out, or failure to finish study)

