5.3 Withdrawal criteria

1. Return to ICU for unstable vital sign or any necessity of surgery.
2. Patient refuse further intervention
3. Physicians judge the patients' condition are not suitable for further intervention.

10. Treatments

6.1.Treatment Administration

1. High protein diet:

The HP groups will maintain unchanged total daily caloric intake and increasing protein content to 1.5g/kg/day. The specific formulas were chosen for their different energy and protein requirement (mainly Nutri-Aid , or NU-PEP HN , according to patients' digestion, and may add Whey-Aid if necessary (above formula are available in CGMH currently)).

We will maintain the nutrition strategies for 21 days according to patients' weaning condition. Protein provision was not reduced in case of renal failure.

2. Core muscle rehabilitation:

Sitting on bedside with or without aids, for 30 minutes, twice per day, 5 days per week, for 3 weeks.

3. Neuromuscular electrical stimulation (NMES):

NMES was applied for 30 min, twice per day, 5 days per week, for 3 weeks, via surface rectangular electrodes. Electrodes were placed on back designed to activate latissimus dorsi and abdominal wall designed to activate the transversus abdominis and internal and external oblique muscles as previously McCaughey et al described ³⁷. Electrical muscle stimulation was performed by using a commercial stimulator (GEMORE, GM300E, Taipei, Taiwan) with biphasic waves at a simulation frequency of 30 Hz and pulse width of 400s, cycling 2s on and 4s off. Electrical muscle stimulation intensity was gradually increased until a visible muscle contraction was observed (median 60 mA [range 50–65 mA].

The subjects in the control group received similar electrode placement and intervention duration, except that the stimulator power was off.

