11.1 Sample size Determination

This is an exploratory research, we determine the enrolled number according to the

number of patients admitted to RCC annually.

Ten patients will be assigned to UC group.

Thirty patients will be included in another 3 group.

A total 100 patients will be enrolled.

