11.3 Analysis Population

All subjects randomized.

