11.4 Procedure for accounting for missing, unused and spurious data

The incomplete clinical data and sequencing data with poor quality will be excluded in the study.

12. Direct access to source data/documents

Investigators permit IRB to access to the source data of experiment for trial-related monitoring, audits and regulatory inspection.

13. Ethical considerations

This study will be conducted according to Taiwan and international standards of Good Clinical Practice for all studies. Applicable government regulations and Chang Gung Medical Foundation research policies and procedures will also be followed.

This protocol and any amendments will be submitted to the Chang Gung Medical Foundation Institutional Review Board (IRB) for formal approval to conduct the study. The decision of the IRB concerning the conduct of the study will be made in writing to the investigator.

All subjects for this study will be provided a consent form describing this study and providing sufficient information for subjects to make an informed decision about their participation in this study. This consent form will be submitted with the protocol for review and approval by the IRB. The formal consent of a subject, using the IRB-approved consent form, will be obtained before that subject is submitted to any study procedure. This consent form must be signed by the subject or legally acceptable surrogate, and the investigator-designated research professional obtaining the consent.

14. Data handling and keeping

Clinical samples will be collected in Chang Gung Medical Foundation. The sequencing data will be stored in computers of laboratory with an electronic encryption. The clinical and source data can only be assessed by clinical doctors and investigators of the study.

15. Financing and Insurance

Apply for CMRP support. The funders had no role in the study design, data collection and analysis, decision to publish, or manuscript preparation.

16. References

Background

Ventilator-induced diaphragm dysfunction (VIDD)

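### The plan promises intention-to-treat on all randomised patients but drops cases with missing data, and has no rule for weaning status after withdrawal or death

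*Combined protocol and SAP*

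**What the plan says.** **Who is analysed.** The statistical methods in the synopsis state: "Analyses of primary and secondary outcomes are performed with the use of time-to-event methods according to the intention-to-treat principle". Section 11.3 gives the analysis population as "All subjects randomized". The synopsis definition of ITT differs slightly: it refers to eligible, consented patients and does not mention randomisation.

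**What happens to missing data.** Item 5 of the synopsis statistics reads: "Omit the cases with missing data and analyze the remaining data". Section 11.4 says: "The incomplete clinical data and sequencing data with poor quality will be excluded in the study". It does not say whether single values or whole patients are removed.

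**How much loss is expected.** Section 4.2 gives an evaluable number of 100 and then "Enrolled Number: 80 (20% dropped out, or failure to finish study". Section 11.1 says "A total 100 patients will be enrolled", so the two labels in 4.2 appear to be swapped.

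**Who withdraws.** The first criterion in 5.3 is "Return to ICU for unstable vital sign or any necessity of surgery". The second is refusal of further intervention, and the third is the physician's judgement that the patient's condition is unsuitable for it.

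**The endpoint.** Section 3.2.1 defines weaning success as five consecutive days off the ventilator. The definition gives no assessment day and no rule for death, withdrawal or unknown status. The schedule in 4.3 has a weaning-rate row, but it supplies none of those rules. Sections 11.2 and 11.2.1 name Kaplan–Meier analysis without a censoring rule. No sensitivity analysis for missing data is planned.

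**The concern.** For a randomised patient whose weaning status is missing, the two instructions cannot both be followed: one keeps the patient and the other removes the case. The plan's own 20% figure means this may not be rare. Return to ICU, surgery and physician judgement are all tied to clinical condition, so withdrawn patients could plausibly wean less often than those who stay. Leaving them out would then raise the reported weaning rate. Censoring them at withdrawal in a Kaplan–Meier analysis has a similar effect, because that method assumes censored patients go on to wean like those still at risk.

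The comparison between arms is also exposed. It is distorted whenever the bias differs between arms, through a different share lost or a different weaning rate among the lost. Because no rule is fixed in advance, the analyst could omit withdrawn patients, censor them or count them as failures. With 10 patients on usual care, reclassifying one of them moves that arm's rate by 10 points.

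**Working it through.** **The plan's own figures.** Sections 4.1 and 11.1 give 10 usual-care patients and, on the reading that matches the stated total, 30 in each of three active arms: 10 + 3 × 30 = 100. A 20% loss leaves 100 × 0.80 = 80. Both figures reproduce. There is no power calculation and no expected weaning rate to reproduce.

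**Formula.** In one arm, let p be the true weaning rate among all randomised, w the share left out, and r the weaning rate among those left out.

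- Reported crude rate = (p − w·r)/(1 − w)
- Bias = w(p − r)/(1 − w)

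Only the overall 20% comes from the documents. Using it as w assumes that dropping out means a missing outcome. The values of p, r and the loss by arm are also assumed.

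**One arm, w = 0.20.** The Kaplan–Meier column takes daily steps, with weaning spread evenly over days 1–28, withdrawals censored evenly over days 1–21, and r = 0.

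| True p | Crude, r = 0 | Kaplan–Meier, r = 0 | Crude, r = p/2 | Crude, r = p |
|---|---|---|---|---|
| 40% | 0.40/0.8 = 50% | 47.1% | 0.36/0.8 = 45% | 40% |
| 50% | 0.50/0.8 = 62.5% | 59.4% | 0.45/0.8 = 56.3% | 50% |
| 60% | 0.60/0.8 = 75% | 72.2% | 0.54/0.8 = 67.5% | 60% |

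**Between arms, no true effect.** The true rate is 50% everywhere (5/10 on usual care, 15/30 per active arm). In (a) and (b) the losses total 20 of 100.

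(a) *Equal 20% loss, different r* (losses 2 + 6 + 6 + 6):
- If 1 of 2 lost usual-care patients and 0 of 6 lost active patients weaned: 4/8 (50%) v 15/24 (62.5%), Fisher p = 0.68.
- If 0 of 2 and 3 of 6 weaned: 5/8 (62.5%) v 12/24 (50%), p = 0.69.

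(b) *r = 0 everywhere, unequal loss* (2 + 3 + 6 + 9): usual care 5/8 (62.5%); active arms 15/27 (55.6%), 15/24 (62.5%) and 15/21 (71.4%). The active arms spread over 71.4 − 55.6 = 15.8 points before rounding error, about 16 (lowest v highest, p = 0.37).

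(c) *More loss, less bias:* w = 0.3 with r = 0.4 gives (0.5 − 0.12)/0.7 = 54.3%; w = 0.1 with r = 0 gives 0.5/0.9 = 55.6%.

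So equal loss does not by itself protect the comparison, and the arm losing more patients is not always the one favoured. With equal true rates, the comparison is unbiased only if w(p − r)/(1 − w) is the same in both arms, for example with equal w and equal r.

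**The case against.** The strongest reply is that stopping the intervention is not the same as a missing outcome. These are inpatients. The synopsis and sections 4.1 and 7 say hospital outcomes, including weaning and mortality, are followed, and two of the three withdrawal criteria speak only of further intervention. Ventilator status may therefore be in the chart for most withdrawn patients, which would bring w, and with it the bias, close to zero. This stands as a limit on the size. It does not settle the point: no section extends follow-up to withdrawn patients, and 4.2 sets the 20% against an evaluable count. Even with complete charts, the handling of deaths and the censoring rule would still be undefined.

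A second reply is that the omission rules may have been meant for the repeated laboratory, ventilator and ultrasound measures; 11.4 even mentions sequencing data, which are not among the scheduled assessments. That may be so, but both rules are worded generally and neither exempts the primary endpoint.

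Third, the magnitudes rest on assumed inputs, and r = 0 is an extreme. With 10 v 30 patients at 50%, the standard error of the difference is √(0.25/10 + 0.25/30) = 0.18, or 18 points, which is larger than the between-arm distortions shown. That is correct, and none of the examples is statistically significant. The exploratory label in 11.1 does not remove the problem, however: with no power basis, the estimated rates are the main product of the trial, and it is these that are distorted.

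**Conclusion.** The concern holds. The text contradicts itself on who is analysed, and it gives no rule for withdrawn, deceased or unknown-status patients on the primary endpoint. If 20% are lost from the weaning analysis, the overstatement at a true 50% runs from 0 points (the lost wean like the rest) through 6.3 (half the overall rate) to 12.5 (none wean). Between arms, the illustrations give distortions of 12.5 to about 16 points with no true effect, in either direction. These are conditional figures: the weaning rates, the rate among those lost and the loss by arm are all assumed, and the bias disappears if outcomes are in fact obtained for everyone. The consequence is distorted estimates rather than false significance at these arm sizes. It should be fixed; confidence in its size is moderate, because actual follow-up after withdrawal cannot be judged from the documents.

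**What to change.** For weaning and mortality, replace the omission rules in the synopsis and 11.4 as follows.

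1. State that withdrawal under 5.3 ends the study intervention, not outcome follow-up.
2. Take ventilator and vital status from the hospital record for every randomised patient, within consent to data use, to one fixed day that lets the five-day window finish. For example: weaning that starts by day 28, the last scheduled visit in 4.3, with status checked to day 28 + 5 = 33. Follow in-hospital mortality to discharge.
3. Analyse all randomised patients as randomised, with the same definition in the synopsis and 11.3.
4. Count as not weaned all deaths before weaning and all patients known to be still ventilated, including those returned to ICU. For truly unknown status, such as transfers out, pre-specify not weaned as the primary rule, with best-case/worst-case and complete-case sensitivity analyses.
5. Do not censor at withdrawal. Treat death before weaning as a competing event, or keep such patients at risk to the fixed day.
6. Report withdrawals, unknown status and reasons by arm, and correct the labels in 4.2.

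**Cost.** Revised wording, submitted to the IRB as section 13 requires for amendments, and a chart look-up for withdrawn patients. Reported weaning rates may be lower. The not-weaned rule can itself bias the comparison: at a true 50% in both arms, with 10% v 30% unknown who wean like the rest, it gives 0.5 × 0.9 = 45% v 0.5 × 0.7 = 35%. The bounds would show this. With 20% unknown per arm and 4/8 v 12/24 observed, the active-minus-usual-care difference runs from 18/30 − 4/10 = +20 points to 12/30 − 6/10 = −20 points. Keeping unknown status rare through the chart look-up therefore matters more than the choice of rule.
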